## **7.3 Handling of Events**

### **7.3.1 Adverse events**

In case of mild adverse events where the patient has only tolerable symptoms, symptomatic treatment or drug discontinuation is not required. When the symptoms affect normal life and are intolerable to patients, treatment discontinuation, delayed chemotherapy, or symptomatic treatment is required.

### **7.3.2 Serious adverse events**

In case of serious adverse events, the treatment should be immediately discontinued, and emergency treatment should be given.

## **7.4 Documentation of Events**

AEs observed during the study should be recorded in the CRF, and those observed within 30 days after the last dose should also be recorded in the CRF if they are related to the study drug. Documentation of AEs should include event description, onset and end time, severity and frequency, whether treatment is required (if yes, the treatments given should be recorded), and whether the AE is related to the study drug as judged by the investigator.

Events should be tracked until resolution. Medical documentation of AEs should be documented in source documents (including the report of test results). If the subjects discontinue treatment due to the end of the study or discharge, the investigator should send the subjects' case summary (including treatment arrangement and instructions on whether continued follow-up is required for relevant AEs) to the physician in charge of continued treatment. The above information should also be documented in the source documents.

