## **5.4 Follow-up**

On-site follow-ups will be conducted 30 days after the last dose at the study site, and safety information (including AE outcome, new SAEs, and adverse events of special interest) will be collected by telephone follow-ups at 60 and 90 days after the last dose, with a time window of  $\pm 7$  days.

If a subject starts a new antitumor therapy within 30 days after the last dose, the follow-up should be completed before the new antitumor therapy.

- ✓ Blood routine: Red blood cell count, hemoglobin, platelet count, white blood cell count, neutrophil count, lymphocyte count;
- ✓ Clinical chemistry: ALT, AST, GGT, total bilirubin, direct bilirubin, AKP, blood urea nitrogen or urea (blood urea nitrogen is preferred), total protein, albumin, creatinine, blood glucose, lactate dehydrogenase, K+, Na+, Ca2+, Mg2+, Cl;
- ✓ Thyroid function: TSH, FT3, FT4;
- ✓ AEs: AEs should be recorded in detail;

Concomitant medication: Concomitant medications are recorded until 90 days after the last dose. Concomitant medications for study drug-related AEs are recorded until 30 days after the last dose.

Survival follow-up will be performed by telephone and other effective methods once a month from the last dose to determine if the subject has initiated new antitumor therapy subsequently. If so, the treatment regimen, as well as start and end time will be recorded and the survival follow-up form will be completed.

For subjects who withdraw from the study due to "non-PD" (such as intolerable AEs), tumor assessment is recommended to be performed according to the frequency of efficacy evaluation specified in this study (every 6 weeks  $\pm$  7 days) during the tumor progression follow-up until PD, death or initiation of new antitumor therapy. The follow-up information should be recorded in the CRF.

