## **5.6 Unscheduled Visits**

During the study, if unscheduled follow-up is required due to AE occurring within 90 days after the last dose or within 90 days before a new antitumor therapy, the following should be recorded:

- ✓ Concomitant medications;
- ✓ Adverse events;
- ✓ All relevant examinations performed (including radiological examination, if any).

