### **7.1 Adverse Events**

AE is defined as any untoward medical occurrence in a subject administered a pharmaceutical product which does not necessarily have a causal relationship with this treatment. AE includes any unfavorable symptoms, signs and diseases temporally but is not necessarily associated with drug administration (worsening of a pre-existing condition during the study is also considered an AE). According to the GCP, the investigator should truthfully record all AEs in the original records and copy them into the case report form (CRF) regardless of their causal relationship with the study drug.

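### Section 7.4 records post-treatment adverse events only if judged drug-related and only to day 30, which conflicts with sections 7.1, 5.4 and 5.6

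*Protocol*

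**What the plan says.** Four sections of the protocol govern what is recorded once dosing stops.

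- **7.1 Adverse Events** tells the investigator to take all AEs from the original records and "copy them into the case report form (CRF) regardless of their causal relationship with the study drug". It gives no end date.
- **7.4 Documentation of Events** opens with "AEs observed during the study should be recorded in the CRF". It then adds that "those observed within 30 days after the last dose should also be recorded in the CRF if they are related to the study drug". Among the items to document for each AE it lists "whether the AE is related to the study drug as judged by the investigator".
- **5.4 Follow-up** sets an on-site visit 30 days after the last dose, with the item "AEs: AEs should be recorded in detail". It adds that "safety information (including AE outcome, new SAEs, and adverse events of special interest) will be collected by telephone follow-ups at 60 and 90 days". These calls are timed from the end of dosing and may fall up to 7 days either side.
- **5.6 Unscheduled Visits** covers AEs that require an extra visit "within 90 days after the last dose or within 90 days before a new antitumor therapy".

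Section 9.3.2 describes the AEs seen in the trial and calculates their incidence. It states no post-dose window.

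**The concern.** The sections give different answers on two questions: whether a post-dose AE must be judged related before it enters the CRF, and how long recording lasts.

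The first matters more. Section 7.4 treats relatedness as something to document for each AE, and in the same paragraph makes it a condition of entry after the last dose. A post-dose AE judged unrelated then leaves no line in the CRF, so nobody can later review that judgement. The trial is open-label with a single arm, and the investigator makes the call. Safety is part of the primary objective (2.1), and without a comparator the descriptive AE incidence is the main safety result. A statistical analysis plan could not repair the gap, because it cannot analyse events that the CRF never captured.

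**Working it through.** No figure in the protocol bears on this, so the check is a comparison of the rules.

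| Section | Events covered after the last dose | End of recording | Relatedness condition |
|---|---|---|---|
| 7.1 | all AEs | none stated | none |
| 7.4, first clause | AEs during the study | the phrase is not defined | none |
| 7.4, second clause | AEs | day 30 | only if related |
| 5.4, on-site visit | AEs in detail | day 30 | none |
| 5.4, telephone | AE outcome, new SAEs, special-interest events | day 90 (±7) | none |
| 5.6 | AEs that require an unscheduled visit | day 90, or the 90 days preceding new therapy | none |

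Four example events, counted in days from the last dose, show where the rules part:

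1. *Non-serious AE on day 20, judged unrelated.* Required by 7.1 and by the 5.4 visit. Not required by the second clause of 7.4.
2. *New SAE learned of at the day-60 call.* Required by 7.1 and collected under 5.4. Outside the second clause of 7.4, whatever its cause.
3. *Non-serious AE leading to an unscheduled visit on day 45.* Required by 7.1 and 5.6. Outside the second clause of 7.4.
4. *AE leading to an unscheduled visit on day 150, with new antitumor therapy on day 180.* The alternative in 5.6 covers day 180 − 90 = 90 to day 180, so it is recorded there. It lies beyond every contact in the 5.4 safety schedule and beyond 7.4. Because the alternative counts back from a date that may be late or never come, it sets no fixed end.

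Other text confirms that the windows were not aligned. Section 7.2 counts some deaths after day 30 as SAEs. Section 5.4 records concomitant medication to day 90, but medication given for drug-related AEs only to day 30.

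**Effect on incidence.** Let n be the number in the safety set and x the number with a given AE when every AE to day 30 is recorded. Let d be the number among these x whose only occurrence is post-dose and judged unrelated. Then

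- all AEs recorded: incidence = x/n
- second clause of 7.4 applied: incidence = (x − d)/n
- difference = d/n.

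The difference is zero or downward, and it falls on the all-cause incidence. The drug-related incidence to day 30 is the same under both rules. The protocol gives no value for d and nothing from which to derive one. As a unit of scale only: if all 39 planned patients enter the safety set, each patient counted in d is worth 1/39 = 2.6 percentage points.

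**The case against.** The best defence is that the first clause of 7.4 already covers the follow-up period, since 5.6 opens by placing AEs up to 90 days after the last dose within the study. Read that way, 7.4 agrees with 7.1 and nothing is lost. But the second clause would then have no purpose. It has meaning only if post-dose events are otherwise outside the first clause. The defence shows that the text is ambiguous and does not remove the conflict.

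Several stronger readings that a reader might infer are not supported:

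- *That days 31 to 90 have no CRF rule.* Section 7.1 is a CRF rule with no end date, and nothing says that 7.4 overrides it. SAEs also have their own reporting route in 7.5 with no relatedness condition, although that is not a CRF entry.
- *That the protocol promises all AEs to day 90.* The calls in 5.4 and the visits in 5.6 cover only the limited groups shown in the table.
- *That the loss can be read from the length of the window.* For k cycles without delay, dosing spans 21k − 7 days, so the 30 days make up 30/(30 + 21k − 7) of the time from first dose to day 30: 30/65 = 46% for k = 2, 30/107 = 28% for k = 4 and 30/149 = 20% for k = 6. These are shares of calendar time under assumed cycle numbers. They are not shares of events lost.
- *That every omitted event costs 2.6 points.* It costs nothing if the patient already had that AE recorded.
- *That patients who stopped for toxicity are affected most.* The protocol does not show this. Sections 4.6.1 and 4.6.2 describe bleeding and thromboembolism as risks that anlotinib increases or may increase, so investigators may well call such events related, and 7.4 keeps related events to day 30.

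**Conclusion.** The conflict is real and should be corrected. To day 30, the relatedness condition in 7.4 contradicts 7.1 and the on-site visit in 5.4. From day 31 to day 90, the 30-day limit in 7.4 does not match the collection that 5.4 and 5.6 provide for, and the alternative in 5.6 has no fixed end.

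The consequence depends on what sites do. Where they apply the second clause of 7.4 as written, post-dose AEs called unrelated are missing from the all-cause incidence in 9.3.2. Where they apply 7.1, 5.4 and 5.6, these events are captured. Where practice differs, recording is uneven. The size cannot be computed from the protocol, and a material bias is not demonstrated. The conclusion rests on taking the second clause of 7.4 to have a purpose of its own.

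**What to change.** Remove the relatedness condition from 7.4 and state one rule there: *All AEs from consent to 30 days after the last dose, and all SAEs, adverse events of special interest and AEs leading to an unscheduled visit to 90 days after the last dose, are recorded in the CRF regardless of causality.* Relatedness stays as an item documented for each event, as 7.4 already requires.

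Then align the rest:

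- In 5.6, use the same 90-day window and delete the alternative that counts back from new antitumor therapy.
- If recording is to stop at the start of new antitumor therapy, say so identically in 5.4, 5.6 and 7.4. Otherwise, record the later events and flag them. Section 5.4 already brings follow-up forward for patients who start new therapy within 30 days, so the wording must fit that.
- Have 7.1 refer to the 7.4 rule for the end of recording.
- In 9.3.2, report all-cause and drug-related incidence separately over the stated window.

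The cost is an amendment to the wording and a few more CRF entries; the visits and calls already exist. All-cause AE rates may come out slightly higher. No dose, schedule or clinical rule changes.

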## **7.5 Reporting of Serious Adverse Events**

In case of any SAEs during the trial, the study site(s) should immediately take measures to ensure the safety of the subjects and report verbally to the administrative

authorities and the sponsor in a timely manner. SAEs should be reported in writing to the Department of Safety Supervision of the National Medical Products Administration, sponsor, principal investigator, the Ethics Committee and local regulatory authorities within 24 hours of their occurrence. The investigator should record the onset time, duration, measures taken and outcome of the SAE on the report, and sign and date the report.

## **8. DATA COLLECTION**

In order to ensure the safety of subjects throughout the study and the accuracy, completeness and reliability of the data, laboratory test reports, clinical records and patient medical records should be archived in the patients' files by the investigator as source documents for the study. The conditions of each patient should be recorded in the CRF, including disease status before, during and after treatment, toxicity, disease-related symptoms, efficacy, and dose adjustment.

## **9. STATISTICAL ANALYSIS**

### **9.1 Overall Design**

This study adopts a single-arm design and data are analyzed by SPSS 22.0 and summarized by descriptive statistics.

### **9.2 Analysis Population**

The analysis population includes the full analysis set, per protocol set and safety set. The total number of enrolled subjects, number of subjects in each set, and number of excluded subjects are recorded to determine the dropout rate.

- Full analysis set (FAS): Data set obtained after excluding very few subjects who have not received the study drug or significantly violated the inclusion and exclusion criteria from the ITT set according to the principle of intention-to-treat

(ITT). Efficacy analysis is performed for all enrolled patients who have received at least one dose of the study drug in this data set.

- Per protocol set (PPS): Data set obtained after excluding all FAS subjects who violated the protocol, including subjects who completed  $\geq 2$  cycles of treatment, complied with the trial protocol, had good compliance, did not use prohibited medications during the trial, and completed the procedures specified in the CRF. Missing data will not be imputed. Treatment efficacy will be statistically analyzed for the FAS and PPS.
- Safety analysis set (SAS): Data set obtained by excluding very few subjects who have not received the study drug or with no safety evaluation data from the ITT set, including all patients who have received at least one dose of the study drug after enrollment and with post-dose safety records. This data set is used for safety analysis.

## **9.3 Main Result Analysis**

### **9.3.1 Statistics and analysis of baseline data**

The results of various parameters before treatment will be described. Categorical data will be expressed in number and percent for each category. Measured data will be expressed in number of cases, mean, standard deviation, median, maximum and minimum.

### **9.3.2 Safety analysis**

The type and severity of AEs (adverse reactions) observed during the trial will be described, including the start and end time, severity, relationship with the study drug, measures taken and outcome. The incidence of AEs (adverse reactions) will be calculated.

### **9.3.3 Efficacy analysis**

In this single-arm study, the efficacy endpoints will be statistically analyzed using

descriptive statistics. PFS, OS, and DOR will be described using the Kaplan-Meier estimator, and median PFS, median OS, median DOR as well as ORR, DCR and 95% confidence interval will be calculated.

## **9.4 End of Study**

The data used for final analysis will be collected until the last patient dies, has PD, or has been enrolled for 60 months, whichever occurs first.

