### **2.2 Secondary Objectives**

- 1) To evaluate the long-term survival of patients.
- 2) To evaluate the quality of life of patients.

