### **2.3.2 Secondary endpoints**

- ORR, PFS, OS, CR, PR and DOR (according to RECIST v1.1)
- Safety and adverse events (according to NCI CTC AE v4.0)
- Quality of life assessment (FACT-H&N.V4 Quality of Life questionnaire)

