### 4.3 Route of Administration

Based on the human pharmacokinetic studies, 12 mg qd for 2 consecutive weeks followed by 1-week discontinuation was generally recognized as the recommended regimen for subsequent studies, and 12 mg qd was the maximum tolerated dose. In addition, the study results showed that the  $t_{max}$  of anlotinib in humans was increased with a high-fat diet as compared to administration under fasting conditions, and drug absorption was slightly reduced (approximately 80% that of administration under fasting conditions). Therefore, anlotinib is recommended to be administered under fasting conditions in subsequent clinical practice.

Anlotinib hydrochloride will be administered orally to all enrolled patients at a dose of 12 mg qd before breakfast, for 2 consecutive weeks, and discontinued for 1 week, i.e., three weeks (21 days) as a course of treatment. Treatment should continue until disease progression or occurrence of intolerable adverse reactions.

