### **6.2.2 Definition of endpoints**

Disease control rate (DCR) is defined as the percent of subjects with complete response (CR), partial response (PR) or stable disease (SD) as the best overall response;

Overall response rate (ORR) is defined as the percent of subjects with CR or PR as the BOR;

Progression free survival (PFS) is defined as the time from enrollment to PD or death due to any cause. For subjects with unknown disease status, PFS refers to the time from enrollment to last the follow-up;

Overall survival (OS) is defined as the time from enrollment to death due to any cause. If it is unclear whether the subject has died, OS refers to the time from enrollment to the last follow-up;

Complete remission (CR) is defined as the percent of subjects with CR as BOR.

Partial remission (PR) is defined as the percent of subjects with PR as BOR.

Duration of response (DOR) is defined as the time from the first documented response (CR or PR) to progressive disease (PD) or recurrence.

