## **10. SCHEDULE OF STUDY**

**Start date of enrollment: March 2019; End date of enrollment: March 2021;** 39 subjects are planned to be enrolled. Expected date of last follow-up: March 2026.

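### Section 9.4 lets disease progression end collection of final-analysis data, which contradicts the overall survival endpoint, the long-term survival objective and the March 2026 follow-up date

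*Protocol*

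**What the plan says.** Section 9.4 (End of Study) states that final-analysis data are "collected until the last patient dies, has PD, or has been enrolled for 60 months, whichever occurs first". It has one rule for all endpoints. It makes no exception for OS and does not define the last patient.

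Other sections plan for survival well beyond progression:

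- Section 2.2 lists as a secondary objective "To evaluate the long-term survival of patients".
- Section 2.3.2 names OS as a secondary endpoint, and section 6.2.2 says: "Overall survival (OS) is defined as the time from enrollment to death due to any cause". Progression neither ends nor censors OS there.
- Section 9.3.3 says: "PFS, OS, and DOR will be described using the Kaplan-Meier estimator", with medians.
- Section 5.4 says: "Survival follow-up will be performed by telephone and other effective methods once a month from the last dose". It does not stop this contact at progression.
- Section 4.3 says: "Treatment should continue until disease progression or occurrence of intolerable adverse reactions". The last dose is therefore usually at or near progression, and most survival contact comes after it.
- Section 10 closes enrolment in March 2021 and gives "Expected date of last follow-up: March 2026".

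**The concern.** Because the first of three events ends collection, and progression normally precedes death, progression is usually the one that operates. The 60-month limit, the only part of the rule that matches the calendar in section 10, would then rarely apply.

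At stake is how much survival time enters the final analysis. Three readings of the rule are possible:

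1. The last enrolled patient triggers the cut.
2. The last of the 39 patients still free of progression triggers it.
3. The rule applies to each patient separately.

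Under readings 1 and 2 a single patient's outcome sets the date for everyone. Under reading 3 nobody is followed past progression.

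**Working it through.** **The plan's own date.** March 2021 + 60 months = March 2026. Section 10 thus agrees with the 60-month limit alone.

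**Inputs.** From the protocol: 39 patients, and enrolment from March 2019 to March 2021 (24 months). It gives no design value for PFS or OS, so I assume median PFS of 3 to 8 months and median OS of 10 to 20. For context, section 1.2 cites median survival of 7 to 11 months with second-line drugs, and section 1.1 cites 20 months for recurrent or metastatic disease overall. Section 1.5 cites PFS of 4.8 months for anlotinib in lung cancer, and section 1.3 cites 7.2 months for a sorafenib combination in this disease. I take uniform accrual and exponential PFS, with median *m*.

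**When the cut falls, reading 1.** The median time from the last enrolment to the cut is *m* itself: 3 to 8 months. The chance that the 60-month limit operates is 2^(−60/*m*), at most 2^(−7.5) = 0.55% (*m* = 8).

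**When the cut falls, reading 2.** For one patient enrolled uniformly over 24 months, the chance of being alive and progression-free *t* months after the last enrolment is

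q = [*m* / (24 ln 2)] × 2^(−*t*/*m*) × (1 − 2^(−24/*m*)).

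The chance that all 39 have progressed or died by then is (1 − q)^39. The median cut is where this is about one half:

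| *m* | *t* | q | (1 − q)^39 |
|---|---|---|---|
| 3 | 10 | 0.0178 | 0.50 |
| 4 | 15 | 0.0176 | 0.50 |
| 6 | 26 | 0.0168 | 0.52 |
| 8 | 37 | 0.0171 | 0.51 |

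At *t* = 60, q = 0.00033 for *m* = 6 and 0.00232 for *m* = 8. The 60-month limit then operates in about 1.3% and 8.7% of trials.

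**Length of follow-up at the median cut.** The first patient is enrolled 24 months before the last.

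| | Shortest potential follow-up (months) | Longest (months) |
|---|---|---|
| Reading 1 | 3 to 8 | 27 to 32 |
| Reading 2 | 10 to 37 | 34 to 61 |
| 60-month limit only | 60 | 84 |

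**Deaths observed (simulation).** Post-progression survival is exponential, set so that median OS takes the assumed value.

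| Median PFS / OS (months) | Reading 1 | Reading 2 | 60-month limit only |
|---|---|---|---|
| 3 / 20 | 39% | 53% | 95% |
| 4 / 11 | 64% | 87% | 100% |
| 6 / 20 | 46% | 79% | 98% |

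Across the scenarios run, the ranges are about 39% to 68%, 53% to 94% and 95% to 100%. The figures depend somewhat on the model. If the post-progression median is instead set to OS minus PFS, 4 / 11 gives 59% and 81%.

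**Kaplan-Meier median OS.** Share of trials in which it is reached, with the standard deviation of the estimate where computed:

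| Median PFS / OS (months) | Reading 1 | Reading 2 | 60-month limit only |
|---|---|---|---|
| 4 / 11 | about 100%, SD 1.92 | about 100%, SD 1.65 | SD 1.63 |
| 6 / 15 | 97.7%, SD 2.66 | 100%, SD 2.33 | 100%, SD 2.33 |
| 3 / 20 | 76% | 94% | 100% |

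**Reading 3.** No simulation is needed. Only deaths without earlier progression count, and everyone else is censored at progression, when the risk of death changes. OS as defined in section 6.2.2 cannot be estimated from such data.

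**The case against.** The strongest reply is that the protocol plainly means to gather survival data. Monthly contact has no stop at progression, and the calendar runs to March 2026, so conduct would probably follow sections 5.4 and 10. OS is also secondary and descriptive, and median OS is the only survival summary that section 9.3.3 names. That median holds up well: at OS of 11 to 15 months it is nearly always reached under readings 1 and 2, with little loss of precision. The 20-month figure behind the worse cases describes recurrent or metastatic disease overall, not patients who have failed two lines.

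Much of this stands and limits the point. A reader might infer more than the documents support:

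- That median OS would not be reached. Under readings 1 and 2 this is a material risk mainly when OS is near 20 months: about 76% to 90% of trials reach it under reading 1, and 94% or more under reading 2.
- That the long-term objective could not be answered at all. This does not follow under reading 2, where most deaths may still be seen.
- That the cut would come at about 6 weeks, the last enrolled patient's first scheduled scan. That is possible under reading 1, but the typical cut is at 3 to 8 months.
- That the primary result is damaged. The disease control rate rests on best overall response and does not need long follow-up.

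The reply does not remove the contradiction. Section 5.4 governs contact with patients, while section 9.4 governs which data enter the final analysis. Followed literally, survival data would be gathered and then left out. Nor is this a detail left to an analysis plan, because the protocol itself fixes the rule.

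**Conclusion.** The point holds as an internal contradiction. A rule that stops at progression cannot serve an endpoint that runs to death, and section 9.4 disagrees with sections 2.2, 2.3.2, 5.4, 6.2.2 and 10. The undefined last patient adds a second fault: the cut-off date is ambiguous and depends on one patient's outcome.

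The damage depends on the reading. Under readings 1 and 2 it is mainly the tail of the OS curve, which the long-term survival objective needs. With the last enrolled patient as trigger, the median cut leaves no follow-up beyond about 32 months. Under reading 3 the damage is complete for deaths after progression.

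The sizes rest on assumed medians and exponential times. With PFS well above 8 months the loss under reading 2 would shrink. The contradiction itself depends on no assumption.

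**What to change.** Remove progression from the rule as it applies to OS, and define the trigger. Suggested wording for section 9.4: *Survival data are collected until all patients have died or the last enrolled patient has been followed for 60 months (March 2026), whichever occurs first.*

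An earlier data cut for disease control, response and PFS is optional. If one is wanted, state it separately with its own trigger; it is not needed to cure the contradiction.

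The cost is one sentence in an amendment. It adds no visits, because the monthly survival contact and the March 2026 date are already in the protocol, and it changes nothing about treatment.
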